### 1.2.3 Human pharmacokinetic profile in NSCLC patients

Tables [1.2.3: 1](#) and [1.2.3: 2](#) show human PK parameters and drug exposure after single dose of [REDACTED], [REDACTED] and [REDACTED] mg Nintedanib in NSCLC patients for the respective trials 1199.0001 [[U05-2191](#)] and 1199.0003 [[U06-1697](#)].

### 1.2.4 Clinical experience with Nintedanib in NSCLC patients

A wide range of Nintedanib monotherapy doses was investigated in phase I and II trials in NSCLC (non-small cell lung cancer) patients (clinical trials 1199.0001 [[U05-2191](#)], 1199.0002 [[c01787114](#)], and 1199.0003 [[U06-1697](#)]), from [REDACTED] to [REDACTED] mg *q.d.* and from [REDACTED] to [REDACTED] mg *b.i.d.* [REDACTED]

[REDACTED]

In the clinical trial 1199.0001 [U05-2191], Nintedanib showed an acceptable safety profile at doses up to 250 mg/day as once daily and 500 mg/day as twice daily administration. All patients who had received at least 1 dose of Nintedanib were included into the safety analysis (n=61). The most frequent adverse events over all treatment courses were gastrointestinal disorders with nausea (80.3%), vomiting (60.7%), diarrhoea (55.7%), fatigue (47.5%), malignant neoplasm progression (44.3%), constipation (31.1%), abdominal pain (27.9%), nasopharyngitis (23.0%), anorexia (21.3%), dizziness (19.7%), cough (18.0%), pyrexia (18.0%), dyspnoea (16.4%), headache (16.4%), pleural effusion (14.8%), CD4 lymphocyte decreased (13.1%), cancer pain (13.1%), dyspepsia (13.1%), hyperhidrosis (13.1%), pruritus (13.1%) and ascites (11.5%). The most frequently reported drug-related adverse events were nausea (68.9%), vomiting (45.9%), diarrhoea (44.3%), fatigue (19.7%), CD4 lymphocytes decreased (9.8%), increased hepatic enzymes (9.8%), dizziness (9.8%), pruritus (8.2%), abdominal pain (6.6%), anorexia (6.6%), dyspepsia (6.6%), headache (6.6%), hypertension (4.9%) and constipation (3.3%). The frequencies of these adverse events and laboratory abnormalities were dose-dependent and increased strongly in doses above the MTD. The vast majority of these adverse events and substantial changes in laboratory parameters were already observed during the first 28-day treatment course with Nintedanib, suggesting that the safety profile does not deteriorate with prolonged application of Nintedanib [U05-2191].

In the clinical trial 1199.0003 [U06-1697], 40 patients were treated at doses of 100 mg (n=6), 200 mg (n=6), 300 mg (n=7), 400 mg (n=16) and 450 mg (n=5) given once a day. To confirm the MTD of twice daily dosing (observed in 1199.0001 [U05-2191]), a further 11 patients were treated at a dose of 250 mg *b.i.d.* following a protocol amendment. Nine patients developed dose limiting toxicity (DLT). The most common DLT was an elevation in liver function tests (8/9 patients). In the 450 mg/day cohort 2/5 patients experienced DLT; hence the MTD of Nintedanib was determined to be 400 mg given once a day. The rate of DLTs decreased by splitting the daily dose of the drug. In the 250mg *b.i.d.* cohort 2/11 patients developed DLTs, reaffirming this dose as the MTD for twice daily dosing. The incidence and severity of Adverse Events appeared to be dose dependent. Most of the reported Adverse Events were of CTC grade 1 or 2. Gastrointestinal disorders (diarrhoea, nausea and vomiting) in 49.3% of patients and increases in liver enzymes in 53.0% of patients were the most frequently reported Adverse Events associated with Nintedanib treatment. The number of reported drug related haemorrhagic events and hypertension was very low (2 and 1 respectively). No treatment-related deaths were reported. Results of the 1199.0003 study indicate that the MTD for Nintedanib is 400 mg *q.d.* or 250 mg *b.i.d.*. At doses ranging from 100 mg to 400 mg *q.d.* or 250 mg *b.i.d.* the drug is generally well tolerated. The dose limiting toxicity in the vast majority of patients is elevation in serum liver enzymes. [U06-1697].

### 1.2.5 Residual Effect Period

The Residual Effect Period (REP) is the period after the last dose with measurable drug levels and/or pharmacodynamic effects still likely to be present.

For this trial using 1 day treatment of [REDACTED] to (potentially) [REDACTED] mg Nintedanib in healthy male volunteers, a REP of 14 days is used, i.e. the individual subject's end of trial is on day 15 following dosing at the earliest and the washout between periods is at least 2 weeks (see [Flow Chart](#)).

## 1.3 RATIONALE FOR PERFORMING THE TRIAL

Ofev® soft capsules dissolve instantly within the gut environment and thus show an IR profile. However, the rapid increase of local drug exposure is associated with increased gut wall toxicity and gastro-intestinal adverse drug reactions such as diarrhoea. In contrast, a constant drug release over a longer period of time is hypothesized to improve gastro-intestinal tolerability. Alteration in the shell's composition may lead to such release profiles of Nintedanib and improve tolerability. Hence, several different tablets are to be manufactured to accomplish a MR of Nintedanib over 24 hours and match the equivalent drug exposures to that of the standard Ofev® treatment. Equivalent drug exposure can be presumed, if the MR formulation is within the same exposure corridor as Ofev®, i.e. equal total drug exposure ( $AUC_{0-24,ss}$ ), non-inferior minimum drug concentration ( $C_{min,ss}$ ) and non-superior ( $C_{max,ss}$ ) peak drug concentration at steady state. Consequently, sufficient efficacy for the MR formulation can be assumed without explicit testing. Since only single dose administration is planned for the MR formulations, the concentration after 24 hours post dose will be measured ( $C_{24}$ ), while  $C_{min,ss}$  as well as  $C_{max,ss}$  for steady state may be simulated in a respective model at the end of trial (e.g. after database lock).

## 1.4 BENEFIT – RISK ASSESSMENT

Participation in this study is without any (therapeutic) benefit for healthy subjects. Their participation in the study, however, is of major importance to improve overall tolerability and treatment success of patients with IPF and ILD. The subjects are exposed to the risks of the study procedures and the risks related to the exposure to the trial medication.

### Procedure-related risks

The use of an indwelling venous catheter or venepuncture for e.g. blood sampling may result in mild bruising, and in rare cases, in transient inflammation of the wall of the vein, or nerve injury, potentially resulting in paraesthesia, reduced sensibility, and/or pain for an indefinite period.

The total volume of blood withdrawn per subject during the entire study will not exceed a volume of 550 mL in a 4-week period. No health-related risk to healthy subjects is expected from withdrawal of this volume of blood.

Electrocardiogram (ECG) stickers on the subjects' chests and limbs may cause some local irritation and may be uncomfortable to remove but subjects will be closely monitored to ensure any local irritation does not persist.

### Drug-related risks and safety measures

Nintedanib, as tyrosine kinase inhibitor with an anti-angiogenic mechanism of action, has been administered only short term to healthy volunteers. Nintedanib has been given in single doses to 240 healthy volunteers (see Section 1.2.2) and has been generally safe and well tolerated. The most common drug-related adverse events were gastrointestinal effects (mainly diarrhoea, nausea and vomiting) and headache. All drug-related adverse events were mild or moderate and fully reversible. The highest dose given so far to healthy volunteers was [REDACTED] mg (after at least 10 h overnight fasting followed by standardised continental breakfast 30 min. before drug administration); this was given (two single doses of [REDACTED] mg each separated by a wash-out phase) to 70 healthy male volunteers in trial 1199-0237 [c08883821]. Results of the trials 1199.0001 and 1199.0003 in cancer patients indicate a maximum tolerated dose (MTD) for Nintedanib IR of [REDACTED] mg *q.d.* or [REDACTED] mg *b.i.d.* Nintedanib IR was generally well tolerated within a dose range of [REDACTED] mg to [REDACTED] mg *q.d.* or [REDACTED] mg *b.i.d.*, while dose limiting toxicity in most patients was elevation in serum liver enzymes [U06-1697]; [U05-2191].

Adverse events as described above can be handled under conditions of a clinical trial. The starting dose of Nintedanib MR is within a supposedly safe and well tolerable dose level, based on experience with healthy volunteers as well as patients. Further dose escalation is not expected to ultimately exceed exposure of tested [REDACTED] mg Nintedanib IR *q.d.* and will only be conducted if previous dose level is considered safe (e.g. by clinical and laboratory assessment) (also see Section 3.1 and 4.1.2). Therefore, no undue risk is expected from trial participation to healthy volunteers with short term administration of Nintedanib.

Intake with food is known to improve tolerability of Nintedanib in patients [U06-1411]. Therefore, in this study Nintedanib will be administered after a standardized continental breakfast and dinner (for reference treatment only). Subjects must consume 100% of the pre-dose breakfast in order to be eligible for dosing. The start and stop time and percentage of the breakfast consumed must be recorded in the source.

Subject selection criteria and pre-dose measurements are suitable to select the appropriate healthy population for this trial. Post-dose safety laboratory includes parameters to assess potential side effects reported after multiple-dose treatment in patient populations.

As Ofev®, a marketed product which contains Nintedanib, has no requirement for precautions with regard to exposure to ultraviolet light, precautions with regard to exposure to ultraviolet light are not considered necessary for subjects enrolled in this study.

### Drug-induced liver injury surveillance

Although rare, a potential for drug-induced liver injury (DILI) is under constant surveillance by sponsors and regulators. Therefore, this trial requires timely detection, evaluation, and follow-up of laboratory alterations in selected liver laboratory parameters to ensure subjects' safety; see also Section 5.2.6.1.4, adverse events of special interest.

### COVID-19 pandemic

Based on the pharmacological mechanism and existing non-clinical, clinical and post-marketing data there is no indication that treatment with Nintedanib may increase the risk of infection with or progression of SARS-CoV-2 infection. Participation in this trial may increase the risk of COVID-19 exposure due to travels to the study site and completion of protocol-defined procedures at the site. A risk management plan has been set up at the clinical site that details precautionary measures (e.g., hygiene rules, wearing of face masks, physical distancing) and screening for SARS-CoV-2 infection.

General risk mitigation against COVID-19 will be implemented in accordance with [REDACTED] monitoring and prevention control measures.

COVID-19 testing may be performed based on current infection rates and availability of tests. If required, testing will comprise an antibody blood test performed at screening, and an antigen polymerase chain reaction (PCR) test or other antigen test performed at screening, the day before admission to each treatment period, and discharge or the day before discharge from each treatment period. Testing time points may be changed and additional time points may be added throughout the study as required. The decision on COVID-19 testing and the definition of the testing time points will be agreed by the study team and documented in the Investigator Site File (ISF) via the Clinical Kick-Off Meeting minutes. The risk mitigation measures, where applicable, will be amended based on emerging government guidance.

### COVID-19 Vaccine-Related Risk

Approved (including health authority conditional marketing optimization) COVID-19 vaccines eg killed, inactivated, peptide DNA and RNA vaccines may be permitted according to the investigator's discretion and as per local guidance. Based on the mechanism of action of Nintedanib, as a tyrosine kinase inhibitor, there is no perceived impact on the safety of the study subjects or on the study objectives for subjects who may receive these vaccines (either first or second doses). It is also very unlikely that administration of Nintedanib would interfere with COVID-19 vaccination response; however, no specific preclinical or clinical investigations have been conducted at this point with Nintedanib.

The emerging safety and efficacy data from millions of vaccinated people, many of whom are elderly and with underlying health conditions and taking multiple concomitant medications, indicate that these vaccines have an excellent safety and efficacy record. In the broader interests of society and to limit the extent of the global pandemic, it is important that subjects should receive a vaccine when it is offered to them.

### Summary of benefit-risk assessment

Taking into account the safety profile of Nintedanib, the safety measures in this trial, and the need for effective treatment of fibrosing interstitial lung diseases, the expected benefit of this trial outweighs the potential risks and justifies exposure of healthy human subjects.

## 2. TRIAL OBJECTIVES AND ENDPOINTS

### 2.1 MAIN OBJECTIVES, PRIMARY AND SECONDARY ENDPOINTS

#### 2.1.1 Main objectives

The main objective of this trial is to assess single dose drug exposure of several newly developed MR formulations of Nintedanib (MR1 and MR2 prototypes) compared to ■■■ mg of Ofev® IR, twice daily (Reference, R) following oral administration.

In trial part 1, four MR prototypes of Nintedanib (prototypes 1 and 2, each with a fast and slow in-vitro dissolution rate) will be tested. Based on pharmacokinetic results, one MR formulation may be selected for subsequent optimisation in dissolution and dose rate to ultimately match exposure corridor of Ofev® IR. The optimised MR formulation will then be evaluated in optional trial part 2. If the pre-selected MR formulation is still not matching the Ofev® IR exposure corridor, an optional trial part 3 is conducted after further optimisation of dissolution profile and dose.

Plasma drug exposure and PK parameters will be assessed after each trial part and MR formulations adjusted accordingly (e.g. coating compositions, drug dose) for the following trial part.

#### 2.1.2 Primary endpoints

The following pharmacokinetic parameters will be determined for Nintedanib:

- AUC0-∞ (area under the concentration-time curve of the analyte in plasma over the time interval from 0 [first dose] extrapolated to infinity which includes also the second Nintedanib dose of the day)

#### 2.1.3 Secondary endpoint

The following pharmacokinetic parameter will be determined for Nintedanib:

- AUC0-tz (area under the concentration-time curve of the analyte in plasma over the time interval from 0 to the last quantifiable data point)
- Cmax (maximum measured concentration of the analyte in plasma within the 24h dosing interval)
- C24 (concentration of the analyte in plasma 24 h after the (first) dose)

#### 2.2.2.2 Safety and tolerability

Safety and tolerability of Nintedanib will be assessed based on:

- Adverse events (including clinically relevant findings from the physical examination)
- Safety laboratory tests
- 12-lead ECG
- Vital signs (blood pressure, pulse rate)

### 3. DESCRIPTION OF DESIGN AND TRIAL POPULATION

#### 3.1 OVERALL TRIAL DESIGN AND PLAN

The study will be performed in healthy male subjects as an open-label, randomised, single-dose study in up to three trial parts in order to compare each of the test treatments (MR1, MR2, MRX) to the respective reference treatment R. The subjects will be randomly allocated to three treatment sequences in trial part 1 and 2 (Latin square design). There will be a washout period of at least 14 days between the treatments, i.e. the morning dose in the preceding treatment period and the morning dose in the following treatment period are separated by at least 14 days.

For illustration of the overall study design, refer to Figure [3.1: 1](#). An overview of all relevant trial activities is provided in the [Flow Chart](#). For visit schedule and details of trial procedures at selected visits, refer to Sections [6.1](#) and [6.2](#), respectively.

#### Trial part 1

Trial part 1 (n=30) will be performed with two parallel groups (cohort 1 and 2, each n=15), each in a randomised three-period crossover design in order to compare MR1 test treatments to the reference treatment R (for trial part 1A) as well as MR2 test.

These treatments will be administered after light fed conditions (light breakfast, additionally light dinner in Reference) and in one of the following three sequences for each group:

#### For Trial part 1A:

R	→ MR1-1	→ MR1-2
MR1-2	→ R	→ MR1-1
MR1-1	→ MR1-2	→ R

For Trial part 1B:

R → MR2-1 → MR2-2  
MR2-2 → R → MR2-1  
MR2-1 → MR-2 → R

A single dose (test treatments) and a *b.i.d.* dose for one day (reference treatments), respectively will be administered as depicted in Figure [3.1: 1](#) above and Table [4.1.4: 1](#).

Decision point: either (a) stop here or (b) proceed to trial part 2 with one selected formulation MR1 or MR2 and release profile in order to optimise dose.

In-study decisions will be made by the safety advisory committee (SAC), which will always comprise the investigator, the sponsor's representative medical monitor or the sponsor's medically qualified designee who is familiar with the study protocol and IB, and a PK expert where appropriate. Formulation and dose selection will only be made after a complete review of all data collected from the previous dose group.

The following in-study decisions will be made:

- Formulation selection
- Dose selection (please see Section [4.1.2](#))

Decision rules: The decision will be based on data of all evaluable subjects (see Section [7.3](#) PKS definition) in each of trial parts 1A as well as 1B and will include the assessment of (i) safety parameters (e.g., AE, ECG, vital signs and safety laboratory data) up to 72 h post-dose, (ii) preliminary pharmacokinetic analysis up to 72 h post-dose.

Criteria to stop particular MR formulation after trial part 1 will be in case one of the below points holds true:

- MR formulation is considered not to be safe (see Section [3.3.4.3](#) for stopping criteria)
- the 90% confidence interval (CI) of the  $AUC_{0-\infty}$  gMean ratio between a MR formulation and Ofev® IR lies completely outside of 95-105% and further optimisation of the formulation with regards to dose and dissolution rate is not expected to improve pharmacokinetic properties, accordingly
- the lower 90% CI of the  $C_{max}$  gMean ratio between a MR formulation and Ofev® IR is >105% and further optimisation of the formulation with regards to dose and dissolution rate is not expected to improve pharmacokinetic properties, accordingly
- the upper 90% CI of the  $C_{24}$  gMean ratio between a MR formulation and Ofev® IR is <95% and further optimisation of the formulation with regards to dose and dissolution rate is not expected to improve pharmacokinetic properties, accordingly

In case no MR formulation fulfils the criteria above the following rule will help in deciding which MR formulation to develop further:

- for  $AUC_{0-\infty}$ ,  $C_{max}$  and  $C_{24}$  the adjusted gMean ratios for each MR formulation as well as the gSE of the difference will be calculated coming from the defined ANOVA model in Section [7.3.1](#).
- for an adjusted gMean ratio >1 the decision value (DV) is defined by gMean ratio\*gSE

- for an adjusted gMean ratio  $\leq 1$  the decision value (DV) is defined by gMean ratio/gSE
- the MR formulation with DV values for  $AUC_{0-\infty}$ ,  $C_{max}$  and  $C_{24}$  closest to 1 will be chosen for further development

Decision outcome: If optimisation is considered possible for at least one of the two MR formulations, further optimisation will be done on the selected formulation(s) and tested in trial part 2.

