#### Trial part 2 (optional)

Trial part 2 (cohort 3, n=15) will be performed as a randomised three-period crossover design in order to compare further prototypes to the reference treatment R.

These treatments will be administered after light fed conditions (light breakfast, additionally light dinner in Reference) and in one of the following three sequences:

R → MRX-3 → MRX-4  
MRX-4 → R → MRX-3  
MRX-3 → MRX-4 → R

A single dose (test treatments) and a *b.i.d.* dose for one day (reference treatment), respectively will be administered as depicted in Figure [3.1: 1](#) above and Table [4.1.4: 1](#).

Decision point: either (a) stop here or (b) proceed to trial part 3 with the optimised formulation in order to optimise release rate and dose.

In-study decisions will be made by the SAC.

Decision rules: The decision will be based on data of all evaluable subjects and will include the assessment of (i) safety parameters (e.g. AE, ECG, vital signs and safety laboratory data) up to 72 h post-dose, (ii) preliminary pharmacokinetic analysis up to 72 h post-dose.

Criteria to stop or to continue particular MR formulation after trial part 2 will be the same as for Part 1 (see above).

Decision outcome: If further optimisation is considered necessary and possible for the selected MR formulation(s) tested in part 2, another prototype will be developed and further tested in trial part 3.

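### Should the Part 1 decision values be scaled to AUC, because dose is tuned only after a formulation is chosen?

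*Protocol*

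**What the plan says.** Protocol Section 1.3 sets the target: "Equivalent drug exposure can be presumed, if the MR formulation is within the same exposure corridor as" the reference. It means equal AUC, a minimum concentration that is not inferior and a peak that is not superior. All three are defined at steady state and no numerical margins are given.

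In Section 3.1 (Trial part 1), each pharmacokinetic stop criterion also requires that "further optimisation of the formulation with regards to dose and dissolution rate is not expected to improve pharmacokinetic properties". A formulation whose AUC ratio is far from 1 can therefore survive if optimisation is expected to help.

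For survivors, "the following rule will help in deciding which MR formulation to develop further": take the adjusted ratio for AUC0-∞, Cmax and C24, multiply it by gSE if it exceeds 1, divide it by gSE otherwise, and prefer the formulation with values "closest to 1 will be chosen for further development". Nothing is scaled to dose or AUC, and no rule for combining the three values is given. The SAP does not describe this step.

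The decision point is to "proceed to trial part 2 with one selected formulation MR1 or MR2 and release profile in order to optimise dose". Section 2.1.1 adds that dissolution may change as well. On process, Section 3.1 states that "Formulation and dose selection will only be made after a complete review of all data collected from the previous dose group". After Part 2, "Criteria to stop or to continue particular MR formulation after trial part 2 will be the same as for Part 1".

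**The concern.** If dose is reset after selection so that AUC matches the reference, Cmax and C24 move with it. What then matters is the shape of the profile, roughly Cmax/AUC and C24/AUC. The DV rule instead scores Cmax and C24 at a dose that may not go forward. With AUC ratios well below 1, a sharp peak lifts a low Cmax ratio towards 1 and is rewarded. With AUC ratios well above 1, a low C24 is rewarded in the same way.

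At stake is the only numerical ranking in the protocol: it could steer Part 2 towards the formulation with the higher peak or lower trough at equal exposure. A steadier release with less gastrointestinal toxicity is the purpose of the trial.

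**Working it through.** **Inputs.** N = 15 per three-way cohort, within-subject gCV 26.5% for Cmax and 12% for AUC0-tz (Protocol Section 7.7). Assumed: 12% also for AUC0-∞, and 20–40% for C24, which is not given. Residual df = 26.

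**Check on Table 7.7: 1.** Precision = exp(t × σw × √(2/15) × √(χ²/26)), with σw = √ln(1 + gCV²), t = 1.7056 and √(χ²/26) = 1.2229.
- gCV 20%: exp(1.7056 × 0.1980 × 0.3651 × 1.2229) = 1.163, as printed.
- gCV 30%: 1.251, as printed.
- gCV 26.5%: 1.2195, which matches the printed limits (97.56/80 = 1.2195). The printed 1.215 is the value for gCV 26%, a slip without consequence here.

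**gSE** = exp(σw × √(2/15)): 1.045 for AUC, 1.100 for Cmax, 1.113 for C24 at an assumed 30%.

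**Can the rule reverse?** Two constructed formulations:

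| | AUC, Cmax, C24 ratios | DVs | Cmax/AUC | C24/AUC |
|---|---|---|---|---|
| A | 0.62, 0.95, 0.70 | 0.594, 0.864, 0.629 | 0.95/0.62 = 1.53 | 0.70/0.62 = 1.13 |
| B | 0.60, 0.58, 0.62 | 0.574, 0.527, 0.557 | 0.58/0.60 = 0.97 | 0.62/0.60 = 1.03 |

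A is closer to 1 on every DV, so it wins however they are combined. Give both shapes an AUC ratio of 1 and the AUC DVs tie. The distances of the Cmax and C24 DVs from 1 become 0.68 and 0.26 for A (1.53 × 1.100; 1.13 × 1.113) and 0.12 and 0.15 for B (0.97/1.100; 1.03 × 1.113). B wins, so the AUC scale causes the reversal.

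**Does it arise with plausible release shapes?** Assumed model: one compartment, half-life 10–15 h (Section 1.2.1), absorption rate 0.3–1 per hour, zero-order release over 2–20 h without lag, reference as two equal doses 12 h apart, same AUC ratio for every candidate. The entries are Cmax / C24 at matched AUC for the release duration picked by the smallest sum of |DV − 1|. The scaled column uses only the DVs of Cmax/AUC (gCV assumed 24%) and C24/AUC (20–40%).

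| AUC ratio | Unscaled, summed | AUC-scaled, summed |
|---|---|---|
| 0.5–0.7 | 0.88–1.01 / 1.10–1.31 | 1.02–1.11 / 0.98–1.02 |
| 1.0 | 1.02–1.11 / 0.98–1.02 | same |
| 1.1 | 1.10–1.16 / 0.90–0.93 | same |
| 1.2 | 1.16–1.20 / 0.82–0.85 | same |
| 1.5 | 1.17–1.32 / 0.67–0.79 | same |

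If the largest of the three distances decides instead, the unscaled rule picks 1.00–1.09 / 0.98–1.10 at every AUC ratio, with no reversal.

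**Does scaling remove the fault?** Closeness to 1 is two-sided; the target is one-sided for peak and trough. With C24 equal and gSE 1.09 (gCV 24%), a Cmax/AUC ratio of 0.70 gives DV 0.70/1.09 = 0.642 (distance 0.358). A ratio of 1.10 gives 1.10 × 1.09 = 1.199 (distance 0.199). The scaled rule picks 1.10, the less favourable peak.

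**The case for a change.** The case for a change is that the reversal is a matter of arithmetic, that no choice of combination avoids it in the example, and that the cost is two derived variables and a sentence or two. Nor does it need extreme figures. In the same model (half-life 12.5 h, absorption rate 0.6), a 4 h release after a 6 h lag gives ratios of 0.62, 0.77, 0.66. A 14 h release without lag gives 0.60, 0.63, 0.62. Matched Cmax is 1.24 against 1.05, yet simulated trials choose the first in 82–89% (sum) or 68–79% (largest distance). With both AUC ratios at 1.0 these fall to 17–22% and 13–24%.

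The existence claim stands, and so does the weakness above an AUC ratio of 1 with summed DVs. Less remains of the rest:
- The 1.53 example lies beyond anything the model produces, even with a lag of up to 8 h, and A has the better matched C24 (1.13 against 1.03).
- The milder pair needs a 6 h lag, whereas Section 1.3 describes constant release over a longer time.
- Section 1.4 speaks of further dose escalation, which suggests AUC ratios below 1. There the model without lag shows no harm.
- At an AUC ratio of 1.2, the 90% CI lies wholly outside 95–105% in about 91% of trials. Such a formulation reaches the ranking mainly because the committee has already judged that optimisation would help.

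Matched ratios read one-sidedly, beside the unscaled ones, would avoid the faults of scaled DVs. That display is optional. The point estimates are the divisions shown above, on figures the committee already has. The committee includes a pharmacokinetic expert where appropriate, and the synopsis plans simulations between parts if appropriate.

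**Conclusion.** No change to the plan is needed. The DV rule can rank first a formulation with a less favourable Cmax or C24 at matched AUC. Scaling the DVs to AUC is a trade-off, not a clear gain. At AUC ratios of 0.5–0.7 with summed DVs it would move the pick from a matched Cmax of 0.88–1.01 to 1.02–1.11, and from a C24 of 1.10–1.31 to 0.98–1.02, the wrong direction on both. It improves matters above an AUC ratio of 1, clearly from about 1.2, and only if the DVs are summed. How they are combined is a gap the committee can fill sensibly.

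These figures rest on the assumed model without lag, the assumed C24 variability and near dose-proportional exposure with an unchanged release shape. The documents do not state the last two conditions for the MR tablets, and Part 2 was to test new prototypes with dose and dissolution both open to change. The MR doses are redacted, so the AUC ratio the sponsor expected is unknown. Single-dose matched ratios are also only a proxy for a steady-state target. SAP Section 4 reports that the trial ended during Part 1 and development stopped, so the point concerns the rule as written.
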